4.10. Data Collection and Participant Follow-up

The number of patients approached, who are potentially eligible, who agree to participate, and who decline participation (with their reason for refusal) will be recorded.

Once participants have provided informed consent, baseline demographics, relevant medical history, resilience status, and details regarding their diagnosis will be collected from the participant, the attending surgeon, their medical record and through physical examination. Participants will also complete the WOSI, Shoulder Activity Scale, EQ-5D, VAS pain score, Patient Satisfaction Scale and ASES questionnaires at the time of enrolment.

For the intervention group only, surgical and peri-operative details will be collected from the attending surgeon and the participant's medical records. Adverse events occurring during the surgical procedure or perioperative period will also be documented.

4.10.1. Follow-Up Visits

Participants will be followed for 24 months post-treatment. All outcome data will be collected at 6 weeks (± 7 days), 6 months (± 30 days), 12 months (± 30 days) and 24 months (± 60 days) post-treatment at regularly scheduled clinic visits. Of note, the first follow-up timepoint (6 weeks) is relative to the initiation of rehabilitation for both groups, i.e. 6 weeks from the date of the first physiotherapy visit. At each time point, participants will complete the WOSI, Shoulder Activity Scale, EQ-5D, VAS pain score, Patient Satisfaction Scale and ASES. Physical examination (PE) will be performed by the operating surgeon or assigned delegate. Shoulder-related adverse events and SAEs will also be documented. In cases where the participant does not return to the clinic or in-person visit is not viable, study personnel will contact the participant by telephone or email. The study questionnaires can be completed by the patient online, through REDCap EDC or by telephone. A missed follow-up form should be completed if the participant misses the follow up visit. An early withdrawal form should only be completed if the participant withdraws their consent. The Schedule of Events (Table 1) details the requirements and procedures for each visit.

4.10.2. Telephone Follow-Up

If a participant is unable or unwilling to return for follow-up in the confines of the allowable ranges of times for each follow-up period, then as much information as possible may be collected by telephone, text, email, or standard mail, per local REB/IRB guidelines for the specified follow-up period.

To maximize the integrity of the data, all possible attempts will be made to collect as much data as possible and to reduce loss to follow-up. If a participant wishes to withdraw their consent from the study, the following strategies will be used to reduce the demands of the study and help to retain the subject:

- Ask the participant if you can still collect clinical data from their medical and hospital charts; and
- Ask the participant if they may be contacted by telephone to ask about the primary and secondary outcomes.

Participant should not be deemed lost to follow-up until the 24-month visit is due and all attempts to contact the participant have been exhausted.

4.11. Early Withdrawal

Participants may decide to withdraw from this trial at any time. If a participant withdraws prior to completing the trial, the study personnel will document the reason for withdrawal and attempt to collect any available outcome data. Participants will not be withdrawn from the study due to lack

of adherence to the study protocol (e.g. participant received wrong treatment arm, missed follow-up visits, etc.).

4.12. Participant Retention

Once a patient is enrolled in the trial, the clinical site will make every reasonable effort to follow the participant for the entire duration of the study period. The expected follow-up rate for this study is greater than 90% based on similar fracture trials performed by the study investigators^{33–35}. Based on this experience, we will implement similar procedures to maintain participant retention which include:

1. Individuals will be excluded if they are likely to present problems with follow-up (refer to exclusion criteria).
2. At the time of consent, each participant will provide the name and address of their primary care physician, and the name, address and phone number of one person at different addresses with whom the participant does not live with who are likely to be aware of the participant's whereabouts as well as their own address and phone number. This information, however, will not be stored in the EDC software and will be only collected on the paper CRFs, for internal use only. The research coordinator will confirm that these numbers are accurate prior to the participant's discharge from hospital.
3. The study coordinator will remind participants of upcoming clinic visits.
4. The study coordinator will contact participants no less than once every three months to maintain contact and obtain information about any planned change in residence.

4.13. Trial Committees

4.13.1 Steering Committee

The Steering Committee will provide guidance and direction; specific responsibilities include reviewing and approving the study protocol and working collaboratively to resolve any challenges that arise during the pilot study. The Steering committee will be comprised of national and international experts in shoulder and orthopaedic surgery and research methodology. The committee will be blinded throughout the trial.

4.13.2. Data and Safety Monitoring Committee

Data and Safety Monitoring Committee (DSMCs) are generally recommended for any controlled trial that will compare rates of mortality or major morbidity. Guidance from the Federal Drug Administration supports that a DSMC is not needed for clinical trials exploring interventions to promote symptom relief (<http://www.fda.gov/RegulatoryInformation/Guidances/ucm12069.htm>). As such, a DSMC will not be used in the pilot trial.

Table 1: Schedule of Events

Assessment/ Procedures	Visit 1: Enrollment/ Screening	Visit 1A: Surgery**	Visit 2: 6 weeks (± 7 days)	Visit 3: 6 months (± 30 days)	Visit 4: 12 months (± 30 days)	Visit 5 24 months (± 60 days)
Screening	●					
Informed Consent	●					
Demographics	●					
Randomization*	●					
Operative Data**		●				
Reoperation**/Re-dislocation Instability			●	●	●	●
Rehab status			●	●	●	●
PROs	●		●	●	●	●
Physical Examination	●		●	●	●	●
Safety Assessment		●	●	●	●	●
Assessment of Crossovers and Treatment Failures		●	●	●	●	●

*For randomized cohort only

**For intervention group only

5.0. STATISTICAL PLAN

5.1. Sample Size Determination

Pilot Study: The feasibility objectives in our pilot study do not lend themselves to traditional power calculations. Sample size is based on the precision around the estimate of compliance of 90%. A sample size of 42 patients will yield a 95% CI of 78 to 96% which we feel is adequate precision. If we account for 15% drop-out / loss to follow-up we require a total of 50 patients. Therefore, we propose a sample size of at least 50 participants (25 participants per treatment arm). We have used similar pilot sample sizes to demonstrate feasibility in our previous multi-centre trials^{33–36}. We will also aim to recruit an additional 50 participants in the non-randomized cohort.

5.2. Statistical Methods

Primary Analysis (RCT) – Feasibility: We will use descriptive statistics to analyze the primary objective of feasibility of this pilot RCT. The data will be presented as point estimates (proportions and 95% CIs) that define the components of the composite measure of feasibility: recruitment, follow-up, crossovers, and operation within 3 months of enrolment. We will use a “traffic light” approach for feasibility analysis to determine if the definitive trial can proceed or will require any modifications.

Secondary Analysis (RCT): Both intention-to-treat and per protocol analyses will be performed. We will use descriptive statistics to summarize the results. Mean between-group differences and corresponding 95% CIs will be reported for all secondary outcomes at each time point. No p-values will be provided given the trial is not powered for secondary outcomes. These outcomes will be exploratory in nature.

Non-randomized Cohort Analysis: Analysis for the non-randomized cohort will be done in a similar manner to the RCT whereby outcomes will be summarized descriptively by preference of treatment of the patient. Given the small sample size, no formal statistical testing will be performed. Data from the non-randomized cohort will be used to inform feasibility of incorporating a non-randomized cohort within this study design. The same data will be collected for both cohorts but will not be combined.

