2.2 Secondary Questions

The secondary objectives of the pilot trial will be the clinical objectives of the definitive trial:

1. Rates of recurrent shoulder dislocations up to 24 months' post-treatment;
2. Symptoms of instability without dislocation up to 24 months post treatment;
3. Clinical outcomes measured by Western Ontario Shoulder Instability (WOSI) Index, American Shoulder and Elbow Society (ASES) score, Shoulder Activity Scale, EQ-5D, Visual Analog Scale (VAS) Pain Score, and Patient Satisfaction questionnaire;
4. Physical examination: range of motion, strength, stability;
5. Return to previous level of activity and work, and;
6. Safety, shoulder-related complications and serious adverse events.

Hypothesis: We believe that the pilot trial will be feasible in our ability to recruit participants rapidly and meet our feasibility objectives.

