4.9. Secondary Outcomes

Secondary objectives are to evaluate:

1. Number of recurrent shoulder dislocations up to 24 months post-treatment;
2. Symptoms of instability up to 24 months post-treatment;
3. Patient reported outcomes include the WOSI Index, ASES score, Shoulder Activity Scale, EQ-5D, VAS pain scale and Patient Satisfaction questionnaire.

- The WOSI is a self-administered quality of life outcome measure designed for clinical trials evaluating treatments for patients with shoulder instability. It has been shown to have high reliability, validity and responsiveness¹¹. The WOSI score is commonly utilized and has been shown to provide excellent ability to detect variability in severity of post-operative instability symptoms including following shoulder stabilization procedures²⁸.

- The ASES score is designed to assess shoulder function including instability²⁹. It allows for patient self-evaluation through 11 items that can be used to generate a score, divided into 2 areas: pain (1 item) and function (10 items).
- Shoulder Activity Scale is designed to assess patient's shoulder activity level. The activity rating is a numerical sum of scores for five activities rated on a five-point frequency scale from never performed (0 points) to daily (4 points).
- EQ-5D is a standardized measure of health-related quality of life and consists of five dimensions: mobility, self-care, usual activities, pain/discomfort and anxiety/depression.
- VAS Pain Score is used to assess pain on a 100-point scale ranging from 0 to 100, with zero (0) representing no pain and 100 representing the worst pain imaginable.
- Patient Satisfaction will be documented on a visual analogue score of 0-100 "How satisfied are you with your medical care?" Rated by the subject with 0 is the least satisfied, 100 the most satisfied.

Functional outcome assessment will be patient-reported on paper using case report forms administered by the study coordinator or delegate at each site.

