4. Physical examination (range of motion and stability): Physical examination following surgery will be performed by the operating surgeon or an assigned delegate and will consist of functional assessment important to patients. Range of motion and shoulder stability are commonly reported outcome measures in the literature when assessing success following shoulder instability surgery^{30,31}. Range of motion will be assessed in forward flexion, abduction, ER and IR. Stability will be assessed primarily via the apprehension- relocation physical examination maneuver which has demonstrated the highest sensitivity in the literature for the diagnosis of anterior instability³². Presence of apprehension will be elicited by bringing the patient's shoulder into a position of 90° of abduction and 90° of external rotation in either the supine or upright position. A positive exam finding is the subjective feeling of impending subluxation or dislocation when in this provocative position. Relocation test is performed, positive test is resolution of feeling of impending subluxation.
5. Return to previous level of activity/sport and work: This outcome will be patient reported at each follow up visit. Time to return to sport will be based on when the patient is cleared by their treating surgeon to return. Time to return to work will reflect duration of work stoppage, if applicable. Specific dates of return to sport/work will be collected on study CRFs.
6. Safety: Rate of major and minor shoulder-related complications and serious adverse events.

Note: Feelings of recurrent instability or re-dislocation, regardless of group allocation and timing of onset, will be considered a treatment failure.

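### Section 5.2 prescribes a mean between-group difference for every secondary outcome, which does not fit return-to-sport and return-to-work times or sparse binary outcomes

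*Protocol*

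**What the plan says.** The secondary-analysis paragraph of protocol section 5.2 begins "Both intention-to-treat and per protocol analyses will be performed" and "We will use descriptive statistics to summarize the results". It then fixes the summary: "Mean between-group differences and corresponding 95% CIs will be reported for all secondary outcomes at each time point". It adds "No p-values will be provided given the trial is not powered for secondary outcomes" and calls these outcomes exploratory.

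Section 4.9 lists the outcomes this covers:

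- **Recurrence:** "Number of recurrent shoulder dislocations up to 24 months post-treatment". Section 2.2 words the same outcome as "Rates of recurrent shoulder dislocations up to 24 months".
- **Instability symptoms.**
- **Six patient-reported scores.** Section 4.10 also collects these at baseline: "Participants will also complete the WOSI, Shoulder Activity Scale, EQ-5D, VAS pain score, Patient Satisfaction Scale and ASES questionnaires at the time of enrolment".
- **Physical examination:** range of motion, and an apprehension-relocation test read as positive or negative.
- **Return to sport and work:** defined as times. "Specific dates of return to sport/work will be collected on study CRFs".
- **Safety:** rates of shoulder-related complications and serious adverse events.

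**The concern.** A mean difference is a natural summary for a score or a joint angle. For a duration it requires every patient to have one, and patients still away from sport or work at a visit do not. Taken literally at each time point, the rule describes only those who have already returned. The arm in which more patients never return can then look faster.

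For complications and other infrequent yes/no findings, the difference in means is a difference in proportions, which is a proper quantity. The usual interval for a mean difference, however, behaves badly when events are few.

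Because the sentence covers all secondary outcomes, this is a rule fixed badly and not a detail left open. A statistical analysis plan that handled these outcomes properly would have to depart from it. At stake is whether the pilot's clinical estimates and intervals can be taken at face value. Section 2.2 says these outcomes are the clinical objectives of the definitive trial.

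**Working it through.** **Inputs from the protocol.** Section 5.1: 50 randomised, 25 per arm, 15% loss, 42 analysed (21 per arm if loss is equal). Section 1.1: recurrence as high as 42%. Section 1.4: a 7-fold lower recurrence after Bankart repair, so 42/7 = 6%. The sentence at issue carries no figure of its own. The section 5.1 figures reproduce: the Wilson interval for 38/42 is 77.9% to 96.2%, and 42/0.85 = 49.4, rounded up to 50.

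**Assumptions not in the protocol.** Return-time medians, shares never returning, exponential timing, non-informative loss, rare-event rates of 4% and 2%, and baseline-outcome correlations of 0.3 to 0.7.

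**1. Return times, horizon L = 24 months.** Let λ = ln 2 / median and π = the share never returning.

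- Mean among returners = 1/λ − L·e^(−λL)/(1 − e^(−λL))
- Restricted mean, everyone kept = (1 − π)(1 − e^(−λL))/λ + πL

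Arm A (median 6, π = 0.10): 1/λ = 8.656 and e^(−λL) = 0.0625.
- Among returners: 8.656 − 24 × 0.0625/0.9375 = 7.06.
- Restricted mean: 0.9 × 0.9375 × 8.656 + 2.4 = 9.70.

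Arm B (median 4, π = 0.30): 1/λ = 5.771 and e^(−λL) = 0.015625.
- Among returners: 5.771 − 24 × 0.015625/0.984375 = 5.39.
- Restricted mean: 0.7 × 0.984375 × 5.771 + 7.2 = 11.18.

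| Assumed case (A vs B) | A − B among returners | A − B, all kept |
|---|---|---|
| Medians 6 vs 4, never 10% vs 30% | +1.7 | −1.5 |
| Medians 6 vs 6, never 10% vs 30% | 0.0 | −3.2 |
| Medians 6 vs 4, never 15% vs 15% | +1.7 | +2.1 |

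The sign reverses in the first case, a real difference is hidden in the second, and the third shows no reversal.

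**2. Sparse binary outcomes.** The interval is p1 − p2 ± t × √{[p1(1 − p1) + p2(1 − p2)]/(n − 1)}. Its coverage was found by summing over all binomial outcomes.

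| Per arm | 42% vs 6% | 4% vs 2% | No events in either arm (4% vs 2%) |
|---|---|---|---|
| 21 | 95.1% | 71.8% | (0.96 × 0.98)^21 = 28% |
| 25 | 95.3% | 77.6% | (0.96 × 0.98)^25 = 22% |

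With no events in either arm, this interval collapses to zero width. A Newcombe interval at 0/21 against 0/21 runs to ±z²/(n + z²) = ±3.84/24.84 = ±15 points, which reflects how little is known.

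**3. Recurrence as a 0/1 outcome, 15% non-informative loss.** The true difference is 42 − 6 = 36 points. With 24λ = −ln(1 − p) and 24μ = −ln 0.85, the share with an observed event is λ/(λ + μ) × (1 − e^(−24(λ + μ))), which is 39.0% and 5.5%.

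- Losses counted as event-free: 39.0 − 5.5 = 33.5 points.
- Event-free losses dropped, observed events kept: 44.2 − 6.5 = 37.7 points.
- Patients followed to 24 months only: 36 points, unbiased under this assumption.

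The handling of losses moves the answer by about 2 points.

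**4. Baseline adjustment of scores.** The standard error is multiplied by √(1 − r²): 0.954, 0.866 and 0.714 for r = 0.3, 0.5 and 0.7, so it is 5%, 13% or 29% smaller. At 21 per arm the unadjusted half-width is 2.021 × √(2/21) = 0.62 SD. It becomes 0.59, 0.54 or 0.45 SD.

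**The case against.** The strongest case on the other side is that this is exploratory output in a feasibility pilot, with no p-values and a stated intention to summarise descriptively. The section 4.8 thresholds concern recruitment, follow-up, time to surgery and crossovers, so no secondary estimate drives a decision. Return is recorded at each visit, so returned or not returned could be compared with everyone included, and nothing says non-returners are dropped. The sign reversal needs unequal non-return. All of this stands and limits the consequence. It does not make a mean definable for patients without a return time.

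A reader might also infer three stronger points that the document does not support.

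- **That the analysis is unadjusted and discards the baseline scores.** Section 5.2 is silent on covariates, and a baseline-adjusted mean difference would satisfy its sentence. Covariate choice may sit in an analysis plan not shown. Under randomisation, leaving baseline out costs precision, not validity.
- **That the recurrence analysis is invalid.** The mean of a 0/1 outcome is a proportion, so the difference is a legitimate risk difference. Its interval covers correctly at 42% against 6%. A 24-month count under the assigned strategy, including any later stabilisation, is also a legitimate target.
- **That these estimates will size the definitive trial.** The protocol does not say so. Carrying them forward is a reasonable guess, no more.

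**Conclusion.** The concern holds in a limited form. A single mean-difference rule for all secondary outcomes is wrong for time to return to sport and work, and its usual interval is unreliable for rare binary outcomes.

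The mismatch for return times follows from the outcome's definition and needs no assumption. Its size does: the +1.7 against −1.5 months rests on the assumed medians and on 10% against 30% never returning. The 72% to 78% coverage rests on assumed event rates of 4% and 2%.

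For recurrence, what remains is smaller: about 2 points on 36 if 15% are lost non-informatively, more if loss is informative, plus two wordings (rates in section 2.2, number in section 4.9) that should be made one. Baseline adjustment is a free gain in precision, not a correction of an error. The consequence is misleading or imprecise exploratory estimates. The feasibility conclusions and the sample size of 50 are unaffected.

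**What to change.** Replace the single sentence in section 5.2 with a rule for each outcome type:

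- **Questionnaire scores and range of motion:** mean difference with 95% CI, with the questionnaire scores adjusted for their enrolment value (ANCOVA, or a mixed model with baseline as covariate).
- **Recurrence, instability symptoms, apprehension and complications:** proportion with at least one event (or a positive finding) per arm, and the risk difference with a Newcombe/Wilson-type 95% CI.
- **Recurrence in addition:** one definition used in both sections 2.2 and 4.9, and Kaplan-Meier cumulative incidence at 24 months to deal with incomplete follow-up.
- **Return to sport and return to work:** Kaplan-Meier proportion returned and median with CI, or restricted mean time where the median is not reached, with non-returners censored at last contact. For work, state that the denominator is those to whom a work stoppage applies.

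The cost is analysis wording and a few lines of code. Return dates and baseline scores are already collected, and the sample size does not change.

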5.3. Frequency of Analyses

There will be only one analysis at the end of the trial.

6.0. DATA MANAGEMENT

6.1. Case Report Forms and Data Transmission

Clinical sites will be provided with the trial CRFs prior to initiation of enrollment. Research personnel at each clinical site will submit the required data, as detailed on the CRFs, to the Methods Centre using the REDCap electronic data capture system. Clinical site personnel will receive a unique login and password for the REDCap system and will be able to view and modify data for participants recruited at their clinical site.

6.2. Data Integrity

The REDCap system uses a variety of mechanisms for checking data at the time of entry including skip logic, range checks and data type checks. Upon receipt of new data, the personnel at the Methods Centre will query all missing, implausible, or inconsistent data. Clinical site personnel will be notified of open queries through regular reports and will be required to respond promptly.

7.0. ETHICS AND DISSEMINATION

7.1. Research Ethics Approval

This protocol will be reviewed and approved by the Hamilton Integrated Research Ethics Board (HiREB) prior to commencement of the trial, and by the local Institutional Review Board (IRB) or Research Ethics Board (REB) of each participating clinical site prior to initiation of trial activities at the clinical site.

7.2. Confidentiality

Information about study participants will be kept confidential and will be managed in accordance with the below rules:

- All study-related information will be stored securely.
- All study participant information will be stored in locked file cabinets and accessible only to authorized study personnel.
- All CRFs will be identified only by a coded participant number.
- All records that contain participant names, or other identifying information (e.g. consent forms and contact information forms), will be stored separately from the study records that are identified only by the coded participant number.
- All electronic databases will be password protected.

If a participant revokes authorization to collect or use personal health information (PHI), the clinical site retains the ability to use all information collected prior to the revocation of participant authorization. For participants who have revoked authorization to collect or use PHI, attempts should be made to obtain permission to collect at least vital status (i.e. primary outcome data) at the end of their scheduled study period.

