4.8. Primary Outcome

The success of the pilot study will be based upon the following *a priori* thresholds:

1. 50 patients recruited within 10 months;
2. 42 of 50 participants (85%) achieving complete follow-up at two years;
3. 85% of patients allocated to surgical intervention receiving surgery within 3 months of enrollment;
4. Less than 5 crossovers* between both groups.

***Note:** Crossovers are defined as either: 1) participants randomized to non-operative management (control group) who choose to undergo surgery in the absence of any feelings of recurrent instability or re-dislocation; or 2) participants randomized to surgical intervention who opt out of surgery prior to surgical intervention and choose to undergo primary non-operative management.

We will confirm feasibility with a “traffic light” approach to determine if the definitive trial will be feasible, require modifications or will not be feasible.

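### Section 7.2 names vital status as the minimum primary outcome data to seek after a participant revokes authorization, but vital status is none of the trial's primary or efficacy outcomes

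*Protocol*

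**What the plan says.** Protocol section 7.2 (Confidentiality) deals with participants who revoke authorization over their health information. The site may keep using what it gathered before the revocation. For the period afterwards, "attempts should be made to obtain permission to collect at least vital status (i.e. primary outcome data) at the end of their scheduled study period". The words at issue are the instruction to "collect at least vital status (i.e. primary outcome data").

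Section 4.8 sets the primary outcome as four feasibility thresholds: "50 patients recruited within 10 months"; "42 of 50 participants (85%) achieving complete follow-up at two years"; "85% of patients allocated to surgical intervention receiving surgery within 3 months of enrollment"; and "Less than 5 crossovers* between both groups". Section 2.1 lists the same four topics as objectives. Section 5.2 names them again as the "components of the composite measure of feasibility: recruitment, follow-up, crossovers, and operation within 3 months of enrolment".

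Two other sections cover participants who leave. Section 4.10.2, on withdrawal of consent, has staff seek continued chart access and also "Ask the participant if they may be contacted by telephone to ask about the primary and secondary outcomes". Section 4.11, on early withdrawal, has staff try to obtain whatever outcome data are still available. Neither mentions vital status.

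**The concern.** The parenthesis in section 7.2 is worded as a definition: it tells site staff that vital status is the primary outcome. That would suit a trial with a mortality endpoint. This is a feasibility pilot in patients aged 14 to 40 whose leading clinical outcome is recurrent dislocation.

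The wording matters because it is an instruction to sites. Someone who has revoked authorization may agree to one small request at most, so the item named as the minimum is the one most likely to be obtained. If that item is vital status, the site learns that the participant is alive. It does not learn whether the shoulder dislocated again, whether it feels unstable, or whether it was operated on. Those facts feed the recurrence and instability outcomes. In the control arm they also decide whether later surgery is a crossover (no preceding instability or re-dislocation, section 4.8) or follows a treatment failure (note at the end of section 4.9).

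**Working it through.** No calculated figure in the protocol rests on this provision, so the check compares the named item with each outcome.

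| Outcome (Protocol section) | What is needed to score it | Does vital status at 24 months supply it? |
|---|---|---|
| Recruitment (4.8, item 1) | Enrolment counts and dates | No; settled at enrolment |
| Complete two-year follow-up (4.8, item 2) | The 24-month outcome data described in 4.10.1 | No; nothing in the text says it suffices |
| Surgery within 3 months (4.8, item 3) | Date of surgery | No; settled within 3 months of enrolment |
| Crossovers (4.8, item 4) | Treatment received and, for a control participant who has surgery, whether instability or re-dislocation came first | No |
| Recurrent dislocation; instability symptoms (4.9, items 1 and 2) | Event and symptom history to 24 months | No |
| Questionnaires; examination; return to activity and work (4.9, items 3 to 5) | Participant report and clinic assessment | No |
| Safety (4.9, item 6) | Complications and serious adverse events | Only a death, since section 7.4.2 counts a fatal event as serious |

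Vital status therefore supplies 0 of the 4 primary criteria and 0 of the first 5 secondary outcome groups. It supplies one part of the sixth. The Schedule of Events (Table 1) has no row for it.

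The three provisions on departing participants compare as follows:

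- Section 4.10.2 (withdrawal of consent): seek chart access and telephone contact on primary and secondary outcomes.
- Section 4.11 (early withdrawal): seek any outcome data still obtainable.
- Section 7.2 (revoked authorization): seek permission for vital status as a minimum, labelled as the primary outcome.

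If a site treats revocation as a form of withdrawal, it holds two differing instructions. If it treats revocation as a separate event, only section 7.2 applies, and that section names the wrong item.

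On scale, each randomized participant contributes 1/50 = 2 percentage points to the follow-up criterion. The threshold of 42 leaves room for 50 − 42 = 8 incomplete participants. (42/50 is 84%, not the 85% printed beside it; reading 85% strictly gives 0.85 × 50 = 42.5, so 43 needed and 7 allowed. This does not affect the present point.) The protocol gives no expected number of revocations, so no total effect can be calculated from it.

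**The case against.** Several points on the other side are sound and limit the finding.

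- **Vital status is not useless.** A reader might infer that it informs no endpoint at all. That is too strong, since a death would count in the safety outcome through the definition of a serious adverse event.
- **The rule is a floor and a request.** Sites are asked to seek permission for at least this item, and nothing stops them asking for more. The phrase also mentions primary outcome data, so a careful site could read it as asking for exactly that. This makes the text ambiguous, but a site still cannot tell from it which data to request.
- **Earlier data survive.** A reader might infer that nothing usable remains for anyone who revokes. Section 7.2 says otherwise. Recruitment is fixed at enrolment, surgery timing is settled within 3 months, and any crossover or recurrence already recorded is kept.
- **Sections 4.10.2 and 4.11 may also apply.** The protocol does not say that revoking authorization and withdrawing are mutually exclusive. The other two sections may fill the gap in practice, but they do not correct section 7.2, and the three still disagree.
- **The follow-up threshold.** A reader might infer that vital-status contacts would be counted as followed and tip the two-year criterion from fail to pass. No passage says that vital status meets that criterion, the number of revocations is not given, and the result would have to lie close to the threshold. A definition of complete follow-up may also stand in a statistical analysis plan not available here. This is a reason to add a clarifying sentence; it is not a demonstrated bias.

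**Conclusion.** The contradiction is real and lies within the protocol. Section 7.2 defines the primary outcome as something that sections 2.1, 4.8 and 5.2 do not contain, and its minimum request differs from what sections 4.10.2 and 4.11 seek. It is more than a slip of wording, because it tells sites which data to request when they may have only one chance to ask.

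The consequence is narrow. It concerns information arising after revocation, in those participants who revoke: mainly recurrence or instability to 24 months, later shoulder surgery, and crossover status. No endpoint definition, analysis method or sample size changes. The conclusion rests on the text alone. The practical loss depends on how many participants revoke and how many of those would allow limited further contact, and the protocol gives neither.

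**What to change.** Reconcile section 7.2 with sections 4.8, 4.9, 4.10.2 and 4.11. Replace vital status and its parenthesis with: *recurrent dislocation or instability status, any shoulder surgery, and treatment received*. Keep the condition that the participant must give permission. Add one sentence stating that vital status alone does not count as complete two-year follow-up.

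The change is a sentence or two in the protocol and the matching site instructions, with no extra visits. Its real cost is approval. It asks for more health information from people who have revoked authorization, so under section 7.3 it may be a change to study procedures that needs a formal amendment, with approval by the coordinating ethics board and each local board. Deleting the mistaken parenthesis alone would more plausibly pass as an administrative correction, but would leave vital status as the minimum item.
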